13.2 Analysis plan

Differences in the primary endpoint will be tested on an intention-to-treat basis using Fisher's exact test. As a secondary analysis, the primary endpoint will also be analyzed with log-binomial regression, adjusted for any observed baseline differences that have occurred despite randomization.

Patients who have received disease-modulating MG treatment as indicated in section 10.7 as "Not allowed" after randomization and before the assessment visit at 16 weeks will be counted as non-responders.

In addition to the primary efficacy variable, a few secondary outcome measures of particular clinical relevance have been selected to reduce the risk of false-positive findings. Differences in the change of these continuous measures will be tested with the Mann-Whitney U-test. P-values will be adjusted with Bonferroni correction for these three tests. To estimate 95% confidence intervals around the difference, linear regression with robust standard errors will be used, without adjustment for the number of tests. Patients who have received disease-modulating MG therapy as indicated in section 10.7 as "Not allowed" after randomization and before the assessment visits at 16 and 24 weeks will be censored from the time these treatments were administered.

A challenge in clinical trials is the management of dropouts, which risks introducing a selection error if response data are only available to the patients who remain in the study. As this study only involves study drug administration at baseline, we expect that the drop-out rate, and thus the need for imputation for those who have left the study, will be limited. If the dropout rate is higher than 10%, imputation will be performed, partly with multiple imputation with explicit modeling of the treatment outcome as a function of baseline variables (age, gender, disease activity), partly through so-called "last observation carried forward", where values for patients who left the study are replaced with their most recently observed value. However, it is very important to emphasize the

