8.4 Study drug administration, baseline (V.0)

Study drug administration is carried out at a ward or outpatient clinic, depending on whether the patient is hospitalized or policlinic.

Inclusion and exclusion criteria are reconciled and QMG, MG-ADL, MG-QOL15, EQ5D are performed and somatic status is checked.

Note that QMG testing should be performed ≥12 hours after last dose of cholinesterase inhibitors.

To reduce the risk of allergic reactions, 1,000 mg paracetamol (Alvedon), 50 mg prednisone (Deltison) and 10 mg Cetirizine are administered at least 45 minutes before the infusion. Blood pressure, pulse and temp are checked before starting the infusion.

Important: Before starting the infusion, take a serum tube for exploratory immunological analysis.

The blood sample is sent to the sample management Karolinska University Hospital Solna, attach study-specific consultant referral.

Study drug is administered as an intravenous infusion (2 mg rituximab / ml, total 500 mg or placebo) with increasing infusion rate for a total of about 150 minutes by the nurse in charge of the infusion with the physician in charge of the infusion as support. See Appendix 3, Mabthera Infusion Monitoring.

Speed of Infusion

0-30 min	50ml/h
30-60	100ml/h
60-90 min	150ml/h
90 min -	200ml/h

In case of allergic reactions, the infusion is stopped temporarily and if necessary, 0.5 - 1 mg clemastine (Tavegyl) iv and / or 100 mg hydrocortisone (Solu-Cortef) can be administered intravenously. If the symptoms subside, the infusion can be restarted at the initial drip rate. In case of more severe reactions affecting systemic condition or with circulatory effects, the infusion should be stopped permanently.

The patient is monitored throughout the infusion and blood pressure, pulse and temperature are checked again after the end of the administration. The patient is then observed for another 60 minutes.

Important: before returning home, make sure the patient has:

- Current contact information
- Informed to contact new / aggravated symptoms urgently, no later than 48 hours.
- Received instructions on medication with Prednisolone schedule if it has been deemed indicated

The prednisolone schedule listed below may, if Prednisolone has not already been started on a purely clinical indication, be initiated immediately after the screening visit, or alternatively the day after administration of study drugs, if cortisone treatment is judged clinically indicated by the treating physician:

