10.8 Clinical worsening, rescue treatments

In case of persistent or worsening MG symptoms, rescue treatment should be considered.

Primarily prolonging or reintroducing Prednisolone up to 40mg / d with a new phasing-out schedule; reduction 5mg / week to discontinuation (total treatment time 8 weeks)

Secondarily:

IVIg: total dose 1g / kg, spread over 2-3 days, alternatively

PLEX: A plasma volume is exchanged 3-5 times over 10-14 days

For more info about the above immunomodulatory therapies and the respective degree of evidence at MG, please see the National MG care program at www.snema.se (tab "Documents")

NOTE! Any newly initiated MG immunotherapy (excluding azathioprine, methotrexate and ciclosporin) or dose increase of Prednisolone> 10 mg / d during weeks 9-24 will by definition be considered rescue treatment. This also includes rituximab.

Protocoll nr: 2015-00887 Date: 2021-04-26

Version 7.0 (ENG) 22(42)

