11.2 Quantitative Myastenia Gravis scale, QMG

The QMG scale is used in the study to evaluate primary, secondary, and tertiary study objectives.

The scale is used for quantitative evaluation of MG status and will be carried out by testers who have not participated in the administration of the study drug. The scale consists of 13 domains that are scored 0-3 as well as information about MGFA and subjective health status.

Evaluations on the scale take about 20-30 minutes to complete and are carried out during visits to the center.

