13.1 Deciding on number of study subjects

Based on results reported in Sanders DB et al.², our own experience, and a shorter phasing out of cortisone than used in most protocols, it is estimated that \leq 40% in the placebo group achieve the primary endpoint of a daily Prednisolone dose \leq 10mg with QMG \leq 4. With 25 patients in each arm, the power will be 0.85 with an alpha = 0.05 for a two-sided test of 80% reaching the primary endpoint of the active arm.

[Note, due to slow recruitment the funder of the study, the Swedish MRC, requested a revised power calculation. March 15th 2018 the following text was submitted, which was approved May 25th 2018:

"The study regards a study drug being administered on only one occasion, with determination of main endpoints at 4 and 6 months, respectively. Possible drop-outs are therefore limited to study participants actively interrupting the study, including the follow-up visits that the protocol stipulates, or that dies before these visits. Of a total of 23 included study participants, none have interrupted. One study participant died due to a medical condition not considered directly related to the study medication. A revised power calculation with the same input variables (without loss) shows that with the same number of patents in each treatment arm: 20 per arm (N = 40), power = 81%; 22.5 per arm (N = 45), power = 85%; 25 per arm (N = 50), power = 89%. Based on interim results, it is therefore reasonable to expect a dropout rate <5%. In order to maintain a power of at least 80% and a certain margin for any minor imbalance in the randomization, n≥45 is needed." The power calculation provided in the paper is based on this revised calculation.]

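### The supportive model for the primary endpoint lets observed imbalance choose its covariates, and the secondary-endpoint regression does not name the V.0 score as a covariate

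*Combined protocol and SAP*

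**What the plan says.** Section 13.2 tests the primary endpoint with Fisher's exact test by intention to treat. It adds a log-binomial regression as a secondary analysis, "adjusted for any observed baseline differences that have occurred despite randomization". No variable, imbalance criterion, maximum number or time of selection is given. The same section does name age, gender and disease activity, but only for a multiple imputation model that applies if dropout exceeds 10%.

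For the three secondary endpoints, "Differences in the change of these continuous measures will be tested with the Mann-Whitney U-test", with Bonferroni correction. For the 95% confidence intervals, "linear regression with robust standard errors will be used, without adjustment for the number of tests". No covariate is listed for that regression.

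The baseline scores exist. Section 8.4 states for V.0: "Inclusion and exclusion criteria are reconciled and QMG, MG-ADL, MG-QOL15, EQ5D are performed and somatic status is checked". The scales are also taken at screening (section 8.2), and section 13.2 does not say which visit change is measured from. Section 7.2 defines the secondary endpoints as scores at a visit, not as changes.

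**The concern.** The adjusted risk ratio will be read as the check on the Fisher result. Under the present wording its model is settled by chance imbalance, judged against an unwritten rule, and section 13.4 starts data processing only after the last patient's last visit. Two analysts following the plan could fit different models and both be compliant. The log-binomial model adds a practical risk: with a continuous covariate such as QMG, the maximum-likelihood fit can give some patient a probability of 1, and the usual standard error is then not available.

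For the secondary endpoints the issue is precision. In a trial of 47, a one-standard-error chance difference in baseline is about 0.29 SD, and a plain change-score comparison carries part of it into the estimate. The scores that would remove it are already collected.

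**Working it through.** **Inputs.** N=47 (section 1), taken as 24/23 under 1:1 allocation (section 8.1). Response rates of 80% and 40% (section 13.1). The plan's revised power reproduces with an unpooled normal approximation: at 22.5 per arm, SE = √[(0.24+0.16)/22.5] = 0.1333; 0.40/0.1333 − 1.96 = 1.04; power 85.1% against the stated 85%. This point does not change that figure, because the primary test is unadjusted. SDs, correlations (rho), covariate slopes and imbalance thresholds are not in the documents and are assumptions below.

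**1. How often would baseline QMG enter?** The standardised difference has SE √(1/24+1/23) = 0.292. Entry probability is p = 2[1 − Φ(threshold/0.292)]; for at least one of three independent variables it is 1 − (1−p)³.

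| Rule | QMG enters | Any of three |
|---|---|---|
| difference > 0.1 | 73% | 98% |
| difference > 0.2 | 49% | 87% |
| difference > 0.5 | 9% | 24% |
| p < 0.05 | 5% | 14% |

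**2. Does it matter for the risk ratio?** Simulation used 500 trials per setting, log-odds slopes of 0 to −0.3 per QMG point, and baseline QMG mean/SD of 9.1/2.3, 11.0/3.3 and 14.5/4.5. Including or omitting QMG moved the risk ratio by a median factor of 1.01-1.07 at 80%/40% and 1.01-1.10 at 60%/40%. Where the standardised difference exceeded 0.5 (9% of trials), the medians were 1.05-1.21 and 1.06-1.33.

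**3. Boundary fits, given that QMG enters.** 41-96% of trials at 80%/40%, 10-89% at 60%/40% and 2-79% at 40%/40%. Poisson regression converged in all. Multiplying by step 1, and treating entry and boundary as independent, the unconditional rate at 80%/40% is 0.05×41% to 0.05×96%, about 2-5%, under p<0.05; about 4-9% under a 0.5 threshold; and 0.73×41% to 0.73×96%, about 30-70%, under a 0.1 threshold.

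**4. Type I error at 40%/40%** (1,500 runs, five baseline covariates with assumed effects, robust Poisson standing in for log-binomial; Monte Carlo SE about 0.005). Unadjusted 0.038, QMG fixed in advance 0.041, covariates picked by imbalance at p<0.10 0.031.

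**5. Width of the secondary intervals.** With k the ratio of follow-up SD to baseline SD, adjusted/unadjusted width = √{k²(1−rho²)/(1+k²−2k·rho)}. At k=1 this is √[(1+rho)/2]: 0.806, 0.866 and 0.922 at rho 0.3, 0.5 and 0.7, or 19%, 13% and 8% narrower. Simulations with bounded integer scores and HC3 standard errors gave:
- similar SDs: 8-24% narrower;
- a 10% tail of large worsening: 2-14% narrower;
- k=1.3 to 1.6: about 13% narrower at best and 2% wider at worst (k=1.6, rho 0.7).

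Coverage was 95.0-96.2% unadjusted and 95.0-96.4% adjusted.

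**6. Should the test change too?** Power at 0.0167 for a 0.7 SD effect, Mann-Whitney against adjusted regression: without the tail, 24-29% vs 44-46% (rho 0.3) and 53-59% vs 70-72% (rho 0.7); with it, 18-20% vs 22-25% and 38-43% vs 31-34%. Neither wins everywhere.

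**The case against.** The strongest reply is that no conclusion of the trial is at risk. The primary test is unadjusted, and a mechanical imbalance rule did not inflate type I error. That stands.

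A reader might infer that the wording amounts to choosing the most favourable model. In the simulation of step 4, picking the best of six models raised the error to 0.077. The plan does not exclude that choice, but it does not plan it either, and nothing in the documents shows that it happened.

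A reader might also infer that the log-binomial analysis will fail in 41-96% of trials. Those rates hold only if QMG enters, which the plan does not say; unconditionally the range runs from a few per cent to about 70%.

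On the secondary endpoints, a reader might infer that the planned intervals are wrong, or always wider than they need be. They are neither: coverage is nominal, baseline already enters by subtraction, and the text is silent on the V.0 score without excluding it. The gain can vanish if follow-up scores are much more variable than baseline. The simulations also keep all 47 patients, whereas sections 8.4 and 13.2 censor patients given non-permitted treatment.

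The change has a cost as well. At equal SDs and a 0.7 SD effect, an adjusted 95% interval disagrees with the Bonferroni-corrected Mann-Whitney result on significance in about 26-40% of trials, against 17-20% for the planned interval. That stands, and the fix has to deal with it.

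**Conclusion.** Minor, and worth correcting. The supportive primary analysis has a data-driven covariate rule with no threshold, so whether QMG is in the model ranges from about 5% to 73% of trials by an unstated choice. If QMG enters, boundary fits are common at the design rates and no fallback is given. The usual effect on the risk ratio is small. For the secondary endpoints, naming the V.0 score is a likely but not guaranteed gain in precision, not the repair of an invalid analysis. The entry rates depend only on the 24/23 split and, for several variables, on independence; the other sizes depend on the assumed SDs, correlations and slopes.

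Timing limits what can be gained. Version 7.0 is dated 2021-04-26, after the stated study period (to Q1 2021), and section 13.1 says: "The power calculation provided in the paper is based on this revised calculation". The documents do not say whether the data had been unblinded, so it cannot be concluded that covariates were chosen with outcomes in view.

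**What to change.** Amend section 13.2 in two places.

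1. Replace the imbalance rule with one fixed covariate, V.0 QMG. It is the baseline of the scale that defines response. At 80%/40% only 24×0.2 + 23×0.6 ≈ 19 non-responders are expected, too few for a long list. Fit it by Poisson regression with robust standard errors, which still gives a risk ratio, or by logistic regression with a standardised risk ratio. Keep adjustment for observed imbalances, including age and gender, as a labelled exploratory analysis.

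2. State that change is measured from V.0, and add each scale's own V.0 score to the robust linear regression. The treatment coefficient is then the same whether the outcome is the score (section 7.2) or the change (section 13.2). Randomisation precedes V.0 (section 8.3), so use the screening score for a randomised patient with no V.0 value. For QMG this is only a substitute: V.0 testing requires at least 12 hours off cholinesterase inhibitors, while section 8.2 asks for at least 6 hours and only on a repeat test.

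Keep Fisher's exact test, and Mann-Whitney with Bonferroni. Report the unadjusted interval beside the adjusted one and state that the intervals are for estimation, not testing; 98.3% intervals are optional.

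Cost: no new data, some rewording and a little extra analysis, plus more frequent disagreement between adjusted interval and test, to be acknowledged in the text. If the data are already unblinded, label both adjusted analyses post hoc and report which covariates were used and why.

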8.1 Study design

The study is a randomized, double-blind, parallel group, placebo-controlled multicenter study aimed at evaluating the safety and efficacy of rituximab (Mabthera) in the treatment of patients with new-onset MG. The study is expected to be carried out at 10 -15 centers in Sweden. In the study, approximately 50 individuals will be randomized 1: 1 to one of two treatment arms, (1) rituximab or (2) placebo infusion (NaCl).

Possible study participants are informed orally and in writing about the study during in- or outpatient care at the respective neurology clinic and can, after signed consent, be included in the study. *No study-related measures can be carried out before the consent is signed.*

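### Section 13.2 corrects the three secondary tests by single-step Bonferroni, which is valid but needlessly strict: Holm gives the same familywise error control and is never less powerful.

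*Combined protocol and SAP*

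**What the plan says.** Section 13.2 sets out one primary test: "Differences in the primary endpoint will be tested on an intention-to-treat basis using Fisher's exact test". Section 13.1 gives its level: "With 25 patients in each arm, the power will be 0.85 with an alpha = 0.05 for a two-sided test".

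Section 7.2 lists three secondary endpoints: QMG at week 24, and MG-ADL and MG-QOL at week 16. Section 13.2 says that these few measures "have been selected to reduce the risk of false-positive findings", and then: "Differences in the change of these continuous measures will be tested with the Mann-Whitney U-test". On multiplicity it says: "P-values will be adjusted with Bonferroni correction for these three tests". The 95% confidence intervals come from linear regression with robust standard errors and are explicitly left unadjusted for the number of tests. All other measures are classed as tertiary or exploratory.

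The plan does not write out the familywise level for the secondary tests; 0.05 is the natural reading. It states no secondary power, effect size, SD or correlation, and no order or gate between the primary and the secondaries.

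**The concern.** The trial is small (N=47) and recruited slowly, so secondary power is scarce. Single-step Bonferroni holds every secondary p-value to 0.05/3, even after one or two of the three hypotheses have been rejected. Holm relaxes the threshold after each rejection at no cost in error control. With Bonferroni, a real effect on muscle fatigue, daily activities or quality of life can miss significance only because a weaker procedure was named.

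One reason to keep Bonferroni would be that its simultaneous confidence intervals match its tests. The plan has given that up by leaving its intervals unadjusted.

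**Working it through.** **Inputs.** Primary alpha 0.05 two-sided (section 13.1). Three Mann-Whitney tests, Bonferroni over three (section 13.2). N=47 (Summary) with 1:1 allocation (section 8.1), taken as 24 versus 23; the exact split is an assumption. Secondary family level 0.05 (assumed). Effects of 0.6 to 1.0 SD and equal correlations of 0.3 to 0.6 between endpoints (assumed).

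**The plan's own figure.** The only stated power is the primary's: 0.85 for 40% versus 80% with 25 per arm. The pooled-variance normal approximation has mean proportion 0.60:

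- (0.40 × √25 − 1.96 × √(2 × 0.60 × 0.40)) / √(0.40 × 0.60 + 0.80 × 0.20) = (2.000 − 1.358) / 0.632 = 1.015
- Φ(1.015) = 0.845, which reproduces 0.85.

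There is no secondary figure to reproduce.

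**The two rules.** Order the secondary p-values p(1) ≤ p(2) ≤ p(3).

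- Bonferroni: reject each p ≤ 0.05/3 = 0.0167.
- Holm: compare p(1) with 0.05/3 = 0.0167, then p(2) with 0.05/2 = 0.025, then p(3) with 0.05, and stop at the first failure.

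Holm's first threshold is Bonferroni's and its later ones are larger, so every Bonferroni rejection is also a Holm rejection. Because the first step is the same, the chance of at least one rejection is identical. Holm's familywise control, like Bonferroni's, holds under any dependence between the tests.

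**Power, simulated with Mann-Whitney tests** (24 versus 23, normal endpoints, correlation 0.3 to 0.6, 20,000 trials per scenario). Figures are power per responding endpoint:

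| Assumed effect | Bonferroni | Holm | Gain |
|---|---|---|---|
| 0.6 SD on all three | 0.31-0.33 | 0.37-0.39 | about 0.06 |
| 0.8 SD on all three | 0.57 | 0.65-0.66 | 0.08-0.09 |
| 1.0 SD on all three | 0.79-0.80 | 0.86-0.88 | 0.07-0.08 |
| 0.8 SD on two only | 0.57 | 0.60-0.61 | 0.03-0.04 |
| 0.8 SD on one only | 0.57 | 0.57 | almost none |

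Power to win on all three rises from 0.26-0.34 to 0.45-0.51 at 0.8 SD, and from 0.56-0.62 to 0.75-0.78 at 1.0 SD. With no effect on any endpoint, the secondary familywise error is the same under both rules, 0.041-0.042.

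**Primary and secondaries counted as one family.**

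- Bound from the nominal levels: 0.05 + 0.05 = 0.10.
- Independent tests at nominal levels: 1 − 0.95 × (1 − 0.0167)³ = 1 − 0.95 × 0.9508 = 0.097.
- Planned tests: Fisher's exact test has an actual size of only about 0.037-0.039 at 23 versus 24. The chance of any false rejection is then 8.1% at correlation 0, 7.8-8.0% at 0.3, 7.5% at 0.5, 6.6-6.8% at 0.7 and 5.5-5.8% at 0.9.

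**Effect of a gate** (normal approximation, 0.8 SD on all three, correlation 0.5). Power per endpoint is 0.637 with Bonferroni as written, 0.714 with Holm, and about 0.645 with Holm plus a gate on the primary, taking primary power as about 0.83. These exceed the Mann-Whitney figures because the approximation is more optimistic. Unadjusted testing would give 0.783.

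**The case against.** The strongest reply is that nothing here is wrong. The primary keeps its 0.05, the secondary family is held at or below 0.05, and Bonferroni is simple and conservative. That stands: this is an improvement, not the repair of an invalid test.

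The reply is also right about the size of the gain. Holm is never worse, but it does not beat Bonferroni in every case. It adds nothing to the chance of at least one success and almost nothing if a single endpoint responds. The larger gains need sizeable effects on all three scales, and the plan does not make winning on all three a success criterion.

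Timing is a fair worry. Version 7.0 is dated 2021-04-26, the stated study period ends in Q1 2021, and section 13.1 already refers to a paper. A late move to a more permissive rule would look poor if results were known. This limits when the change can be made; it does not make Bonferroni the better procedure.

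A reader might go further and infer that the plan breaches a 5% error rate because the secondaries are not tied to the primary, putting the overall rate at 8-10%. The documents do not support this. They make no promise of joint control. The stated aim of reducing false positives explains why the secondary list is short, and a short list serves that aim. The 8-10% range also relies on nominal levels; with the planned tests it is about 7-8% for correlations up to roughly 0.7, and lower beyond that.

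**Conclusion.** The point holds as a free improvement. Single-step Bonferroni on the three secondary tests is valid but needlessly strict, and with unadjusted intervals nothing is lost by using Holm. Holm's validity and its never being less powerful need no assumptions. The size of the gain does: about 6 to 9 points per endpoint at 24 versus 23, for effects of 0.6 to 1.0 SD on all three endpoints and correlations of 0.3 to 0.6. It shrinks to 3-4 points if two endpoints respond and to almost nothing if one does. Holm also recovers only part of what adjustment costs.

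The missing link to the primary is an unstated scope, not an error. A gate would hold the four-test error at or below 5%, but it would take back most of Holm's gain and rule out any confirmatory secondary claim after a failed primary. That is a choice for the sponsor. The primary analysis is unaffected either way.

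**What to change.** In section 13.2, name the Holm correction instead of the Bonferroni correction for the three secondary tests, and write out the family level (two-sided 0.05). Report Holm-adjusted p-values: the running maximum of 3p(1), 2p(2) and p(3), each capped at 1. The confidence intervals stay as planned.

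This costs one sentence, no patients and no data. The condition is that the change is dated before unblinding. If that is no longer possible, keep Bonferroni as the pre-specified result and show Holm only as a labelled supplement.

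Optionally, and separately, add a sentence on how a significant secondary result will be described if the primary fails. The Holm change does not depend on it.

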7.2 Secondary endpoints

QMG scores at 24 weeks after treatment

MG-ADL scores at 16 weeks after treatment

MG-QOL scores at 16 weeks after treatment

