Starting dose 40 mg / day, with tapering of 5 mg / week until discontinuation.

For patients already on Prednisolone before screening, the pre-screening dose may be increased to 40 mg / day with subsequent tapering according to the above schedule.

To reduce the risk of study endpoints being affected by another MG-specific treatment, such treatment should be given after randomization in accordance with section 10.7, Permitted / non-permitted treatment at different times.

If the cortisone dose can not be reduced due to persistent or worsening clinical symptoms, you may first choose to increase the dose of Prednisolone and make a new plan for phasing out or, secondly, to give rescue treatment with IvIg or PLEX.

Immunosuppressive therapy (azathioprine, ciclosporin, MMF, methotrexate) can be started if indicated from 12 weeks after randomization. Pulse cures with cortisone should not be given after randomization. In cases where the study physician for medical reasons considers that the above treatments are insufficient or inappropriate, other treatment may also be considered, including rituximab. The patient will then be classified as a non-responder in the primary outcome measure and censored in the secondary outcome measures.

Protocoll nr: 2015-00887 Date: 2021-04-26 Version 7.0 (ENG)

7.0 (ENG) 16(42)

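### Section 13.2 censors the secondary outcomes at a non-permitted treatment, which in fixed-visit tests drops those patients and leaves groups selected on outcome

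*Combined protocol and SAP*

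**What the plan says.** Section 7.2 lists three secondary endpoints, each tied to one visit: "QMG scores at 24 weeks after treatment", and MG-ADL and MG-QOL at week 16. Section 13.2 gives the test: "Differences in the change of these continuous measures will be tested with the Mann-Whitney U-test", Bonferroni-adjusted for three tests. Confidence intervals come from linear regression with robust standard errors.

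For patients given a treatment that section 10.7 does not allow, section 13.2 says that those treated "before the assessment visits at 16 and 24 weeks will be censored from the time these treatments were administered". Section 8.4 has a matching sentence, attached there to other treatment given when the listed options do not suffice: "The patient will then be classified as a non-responder in the primary outcome measure and censored in the secondary outcome measures".

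Missing data are handled separately in section 13.2: "If the dropout rate is higher than 10%, imputation will be performed". One method is multiple imputation from baseline variables. The other is last observation carried forward, "where values for patients who left the study are replaced with their most recently observed value".

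**The concern.** Censoring belongs to methods that use follow-up time. Here the outcome is one number per patient at one visit, and no time-to-event or repeated-measures model is planned for it. A patient whose scores after a given date are unused has no week-16 or week-24 value and so falls out of both the test and the regression.

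The loss is not random. Sections 8.4 and 10.8 tie the treatment to persistent or worsening symptoms, so the patients removed tend to be those doing badly. Section 13.2 itself warns of selection error when response data exist only for those who remain. All three secondary tests are exposed.

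**Working it through.** **1. Does another rule supply a value?**

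| Question | Documents |
|---|---|
| Value for the primary endpoint | Defined: non-responder (8.4, 13.2) |
| Value for the secondary outcomes | None given |
| When imputation starts | Dropout above 10%. Of 47: 0.10 × 47 = 4.7, so 5 or more |
| Expected dropout | Below 5% (13.1): 0.05 × 47 = 2.35, so at most 2 |
| Who counts as a dropout | Active withdrawal or death (13.1), not rescue |
| Do treated patients stay? | Yes. Visits continue (8.5), and follow-up stops only if it would harm the patient (9.3) |

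Imputation therefore does not reach these patients. If it were stretched to them, multiple imputation would use baseline variables only. The last earlier score would be week 4 for the week-16 outcomes, and week 4 or week 16 for week-24 QMG.

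**2. How large could the effect be?** The plan has no figure for the secondary outcomes to reproduce; section 13.1 covers only the primary. All inputs below except N = 47 and the 0.05/3 level are assumptions: 23 placebo and 24 active patients, SD of week-24 QMG change 4, true difference 3.0, and correlation ρ between the treatment trigger and the week-24 change of 0.86, 0.5 or 0.3. The level is 0.05/3 = 0.0167.

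If a fraction q is treated and dropped, let z = Φ⁻¹(1 − q). The mean of those left looks better by ρ × SD × φ(z)/Φ(z). With one trigger cut-off for both arms, z(active) = z(placebo) + ρ × 3/4.

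Example, q = 20% on placebo, ρ = 0.86:
- Placebo: z = 0.842, φ/Φ = 0.350, shift 0.86 × 4 × 0.350 = 1.204.
- Active: z = 0.842 + 0.645 = 1.487, so 6.9% treated, φ/Φ = 0.142, shift 0.488.
- Difference left: 3.0 − (1.204 − 0.488) = 2.28.

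Results for ρ = 0.86 / 0.5 / 0.3. Patients dropped = 23 × placebo rate + 24 × active rate. Power is from 3,000 simulated trials per scenario (Monte Carlo error about 0.01).

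| Placebo treated | Active treated | Dropped of 47 | Difference left | Power, exclusion |
|---|---|---|---|---|
| 5% | 1.1 / 2.2 / 3.1% | 1.4 / 1.7 / 1.9 | 2.7 / 2.9 / 3.0 | 0.45 / 0.47 / 0.48 |
| 20% | 6.9 / 11.2 / 14.3% | 6.2 / 7.3 / 8.0 | 2.3 / 2.7 / 2.9 | 0.30 / 0.37 / 0.37 |
| 40% | 18.5 / 26.5 / 31.6% | 13.6 / 15.6 / 16.8 | 1.9 / 2.6 / 2.9 | 0.20 / 0.25 / 0.26 |

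With all patients' scores and no rescue benefit, power is about 0.50. At low ρ most of the loss comes from fewer patients, not from bias.

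**3. No true difference.** With equal treatment rates, exclusion rejects 0.012 to 0.016, so the error rate is kept. At 40% against 10%, φ/Φ is 0.644 and 0.195, and the false difference is ρ × 4 × (0.644 − 0.195) = 1.54 / 0.90 / 0.54 in favour of the arm with more rescue. The rejection rate is 0.11 / 0.03 / 0.02 against 0.0167. At 20% against 5% it is 0.044 / 0.022 / 0.018.

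**4. The alternatives, same inputs.**
- *Observed scores, true difference 3.0.* With a 3-point rescue benefit, power is 0.45–0.49 (20% placebo rescue) and 0.44–0.45 (40%). With 6 points it is 0.35–0.37 and 0.26–0.29.
- *Observed scores, no difference before rescue, 40% against 10%.* The false difference is 0.30 × benefit: 0.9 or 1.8 points, again favouring more rescue. The rejection rate is 0.05–0.07, or about 0.15–0.30.
- *Worst rank, true difference 3.0.* Power is 0.50 / 0.38 / 0.29 (20%) and 0.45 / 0.27 / 0.17 (40%).
- *Worst rank, no difference in scores, 40% against 10%.* It rejects 0.07–0.18, favouring the arm with less rescue.

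**The case against.** The best defence is that the rule has a meaning and a purpose. Scores after the treatment are not used, and section 8.4 says it wants to limit the influence of other MG treatment on the endpoints. That much stands: a reader might infer that the rule is wholly undefined, but its plain sense is clear. The defect is what that sense does in a fixed-visit test.

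A reader might also infer that nobody can tell whether IVIG or PLEX in weeks 9–24 triggers the rule. The documents do not support that for the analysis: section 13.2 points to 10.7, which lists both as not permitted in those weeks. The conflict lies in the treatment sections. Section 8.4 offers the option "secondly, to give rescue treatment with IvIg or PLEX" and 10.8 does likewise, while 8.4 also says "such treatment should be given after randomization in accordance with section 10.7".

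Nor are observed scores always better than exclusion. With a true difference of 3.0, rescue fixed at 40% against 10% and a 6-point benefit, the observed difference is 3.0 − 0.30 × 6 = 1.2 and power is 0.09 / 0.08 / 0.07, against 0.09 / 0.19 / 0.24 with exclusion. The case for change is a defined question in the randomised groups, not an assured gain in power.

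Finally, materiality is unknown. IVIG and PLEX are unrestricted until week 8, so before the week-16 outcomes they can trigger the rule only from week 9. The primary endpoint has its own defined rule.

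**Conclusion.** The concern holds in this form: followed as written, the rule removes patients from the secondary tests because of how they are doing, and nothing else in the plan puts them back. This should be fixed. It does not affect the primary analysis.

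The size cannot be read from the documents. The figures above hold only under the assumed SD, effect, correlation and treatment rates, and only week-24 QMG was simulated. At 5% placebo rescue the loss is slight.

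A reader might infer that the rule favours rituximab or generally inflates false positives. Neither follows. If rescue is commoner on placebo, exclusion works against rituximab; with equal rates and no effect, the error rate is kept.

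**What to change.** **Analysis rule.** Replace the censoring sentence in 13.2, and its counterpart in 8.4, with a rule that keeps every randomised and treated patient in the secondary tests and gives each affected patient a stated value. Two options are defensible:
- the observed week-16 or week-24 score, regardless of other treatment; or
- a worst rank, matching the primary's non-responder rule.

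State which question is being answered, name one option as main before unblinding, and report the other and the exclusion analysis as labelled sensitivity analyses. Give the number of affected patients per arm. State how deaths before the visit are handled: section 13.1 records one among the first 23 (1/23 = 4.3%), below the imputation trigger.

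**Timing.** Version 7.0 is dated 26 April 2021, after the stated end of the study period in Q1 2021. If the data are already unblinded, keep the planned analysis and add the all-patient analyses as labelled sensitivity analyses.

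**Cost.** Visits continue after other treatment, so the scores should exist and no new data are needed. Observed scores include rescue benefit and can favour the arm with more rescue. Worst rank counts need for treatment as outcome, loses power when rescue is weakly related to the score, and gives the planned regression no natural score to use.

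**Separately**, say whether prednisolone above the 10.7 maximum in weeks 9–24 triggers the rule: 10.8 calls it rescue, but 10.7 does not list it as not permitted. Reconcile 8.4, 10.7 and 10.8 on three points:
- IVIG/PLEX in weeks 9–24;
- MMF, which 8.4 and 10.7 allow but 10.8 leaves out of its exceptions to rescue;
- the start of immunosuppressants, week 12 in 8.4 and week 9 in 10.7.

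This point does not say which treatment rule is right. Significant changes to the protocol may need approval under section 15.1.
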